The American Indian and Alaska Native (AI/AN) population is growing 3 times faster than the US all-races population. The number of AI/ANs aged 65+ is expected to triple to 1,624,000 by 2050, while the number of those aged 85+ will increase 7-fold to 300,000. These trends raise concerns about proportionate increases in Alzheimer's disease and related dementias (ADRD) among AI/AN elders, and concurrent demands for ADRD healthcare and services. Many AI/ANs obtain healthcare through a fragmented system that offers minimal geriatric or specialty care and creates barriers to obtaining high-quality care, resulting in late or under-diagnosis and inadequate care for ADRD. AI/AN elders typically receive their healthcare from primary care physicians (PCPs), who often lack the training and resources needed to diagnose and manage ADRD. The focus of the 2016 Alzheimer's Disease-Related Dementias Summit was on improving specialty skills in the community by training health professionals in dementia diagnosis, care, and research. PCPs are especially well-placed to detect mild cognitive impairment, which is often undiagnosed. While studies suggest that clinic-level interventions can improve ADRD diagnosis and care.

no pragmatic trial has focused on facilities or PCPs that serve Al/ANs. In partnership with an urban clinic serving Al/ANs, we therefore designed "INdians Transforming Alzheimer's Care Training" (INTACT), a clinic-level intervention to improve ADRD diagnosis and quality of care for Al/ANs. The active principal component of INTACT is PCP training in screening, diagnosis, and care for ADRD. Other elements include patient and family education, culturally informed videos, and brochures to create a "dementia-friendly clinic". **First**, we will conduct key informant interviews with PCPs in rural clinics to adapt the existing version of INTACT for delivery in rural settings. **Second**, we will test INTACT with a group-randomized trial at 28 urban or rural clinics that provide primary care to Al/ANs using a wait-control design. Data collection will rely on electronic medical records for clinic- and patient-level outcomes, and on self-report questionnaires at baseline and follow-up for PCP outcomes. Patient outcomes will additionally be assessed by manual chart review to document adherence to quality of care metrics for Al/ANs with diagnosed ADRD.

Specific Aims

- 1. Adapt INTACT for use in clinics serving AI/ANs.
- 2. Conduct a group-randomized trial to test INTACT's effects on PCP knowledge of ADRD, care confidence, and practice behavior.
- 3. Evaluate INTACT's effect on clinic-level outcomes (new diagnoses) and patient-level quality of care outcomes (e.g., treatments commonly used for ADRD).

The rapid growth of the elderly Al/AN population forecasts a ballooning number of Native elders at risk of ADRD. This study will be one of the few trials of a clinic-level intervention that foregrounds PCP education and training to improve ADRD care, and the only one designed for Al/AN communities.

Study Design

In this study, the research team will use **key informant interviews** to adapt the existing intervention to optimize its benefits for clinics serving Al/ANs. Next, the team will conduct a Group-Randomized Trial (GRT) with 28 urban or rural clinics that serve Al/ANs across the US. INTACT will be randomized at the clinic level (immediate intervention or waitlist control arm) and delivered to PCPs in clinics, with most outcome data derived from Electronic Health Records (EHRs.) Outcomes will be evaluated at the levels of clinic (new ADRD diagnoses), PCP (knowledge and self-efficacy for diagnosing and caring for Al/AN patients with ADRD), and patient (quality of care metrics for patients with diagnosed ADRD).

AIM 1: ADAPTING INTACT

INTACT adaptation will be done in 3 steps:

- 1) Adapt educational materials for Al/AN elder patients and caregivers
- 2) Adapt the UW Medicine Cognition in Primary Care Program for clinic serving Al/AN populations
- 3) Develop material to be used in the INTACT GROUP-RANDOMIZED TRIAL

Drs. [name] (WSU) and [name] (UW) will lead the adaptation of INTACT. They will oversee the key informant semi-structured interviews and work with the Recruitment and Engagement Core to adapt the Washington State Dementia Action Collaborative: Dementia Road Map brochure to be distributed to patients and caregivers, as well as the training material for primary care providers and guidelines for clinic on how to implement the INTACT program.

AIM 2: GROUP RANDOMIZED TRIAL

Study Design overview

The INTACT team will conduct a **group-randomized trial** (GRT) to test the effectiveness of the INTACT program, a culturally informed primary care provider training and clinic level workflow intervention for detection and appropriate management of Al/AN patients with Mild Cognitive Impairment (MCI) and ADRD in 28 urban and rural clinics serving Al/ANs. The clinics are the primary unit of randomization. Within each participating clinic, PCPs who are routinely seeing Al/AN patients ages 55 years and older will be recruited for data collection at baseline and 1-year follow-up. Each clinic will be randomized either to the immediate intervention or to a wait-list control arm. Data will be collected from PCP questionnaires, EHR data extraction and manual medical chart reviews. At the clinic level, we will rely on EHRs to document INTACT's effect on new ADRD diagnoses. At the PCP level, we will test whether INTACT increases knowledge and confidence in dementia assessment, ADRD care, and caregiver support. Patient-level data will be collected from the EHR and by manual chart review.

Once enrolled, clinics will complete a clinic profile interview and clinic and patient population information form, PCPs will be consented and complete a baseline survey. Next the clinics will be randomized into the immediate intervention or the wait-list control arms. Data collection will be conducted at baseline and 1-year follow-up. After completing the 1-year study period, clinics in the wait-list arm will have the opportunity to receive the INTACT intervention.

[figure not shown]

Figure 1: INTACT study flow chart

Recruitment

We will start our recruitment effort first with the clinics who have expressed an interest and provided a letter of support at the time of the grant proposal development. We will continue to reach out to new clinics, via NW HERON, a Washington based PBRN, and IREACH networking or are being recommended by a partner clinic or collaborator.

The study participation will last one year and it will be implemented in a staggered fashion creating at least three cohorts. Each cohort will be comprised of at least two clinics.

Clinic eligibility criteria

To be eligible to participate in INTACT a clinic must be:

- 1. A primary care clinic
- 2. Have at least 20 Al/AN active patients 55 years or older
- 3. Have an EHR system
- 4. Not intending to change EHR systems in the next year
- 5. Willing to conduct a total of 40 limited patient chart reviews to assess quality of care metrics for Al/AN patients with MCI and ADRD, staff permitting

IMPORTANT NOTE: power calculations assumed an average of 5 PCPs and 50 patients per clinic at each data collection; the actual numbers could be higher or lower in any given clinic. Therefore, the minimum criteria of 20 Al/AN patients 55 years or older and may be decreased or increased depending on average reached and success of recruitment efforts. We will check the average and the potential need to adjust this criterion approximately every 6 clinics.

PCP approach and eligibility

To be eligible to participate in the baseline and follow-up surveys a primary care provider must be 1) currently employed at a participating clinic, 2) have a title of MD, DO, Nurse Practitioner, or PA, and 3) regularly provides care to Al/ANs aged 65 and older.

Clinic's enrollment implies the involvement of all their PCP's in the study. Clinic leadership will announce their participation in INTACT and will encourage all PCPs to participate. Our team will send an invitation email using to the PCPs that will describe the study, what they will be asked to do and that their participation is voluntary. The email will also contain a link to the REDCap e-Consent form and survey. We will send one follow-up email to PCPs who have not consented two weeks after the initial email. No response to our invitation email will imply a refusal to participate. To protect PCP confidentiality and to protect them from coercion from the clinic leadership, or potential perception of, we will not share with the clinic's leadership the name of the participating PCPs.

IMPORTANT NOTE: This study is conducted at the clinic level, any PCPs employed at the clinic can join the study at any time. All eligible PCPs will be able to participate in the study at any point. Those joining after randomization will not be asked to complete the baseline survey.

Clinic Onboarding

The clinic onboarding process involves conducting a clinic profile interview and recruiting PCPs. Once a clinic has agreed to participate, Drs. [name] and [name] will conduct an in-depth clinic profile interview and Drs. [name] and [name] will work with clinic staff to clearly communicate required elements of data collection.

Clinic Profile Interview

Prior to starting data collection and delivering the INTACT intervention program, Drs. [name] and [name] will conduct a Clinic Profile Interview to learn about the clinic's set up, unique organizational and clinical workflow features, current protocol, and practices with ADRD, the clinic and local resources,

and their Al/AN patient population, The information will be used to tailor the implementation of the INTACT intervention at the PCP and clinic level, and EHR data extraction procedures.

Randomization

Randomization will occur at the clinic level after completion of the PCP baseline data collection. Clinicand patient-level data collection rely on EHR queries and manual chart review, and it is not logistically feasible to complete these before randomization. Clinics will be randomized in batches with at least 2 clinics per batch, to ensure simultaneous launch with at least one clinic in each study arm.

Note on immediate intervention arm engagement

For the 14 clinics randomized to the immediate intervention arm, clinic leadership will announce their participation in INTACT and will encourage all PCPs to participate in the programmatic elements for professional development and ADRD-related capacity-building. All PCPs employed at the clinic at any time during the 1-year study period are invited to engage with all aspects of the intervention, including those who are newly hired during the study period. For clinics in the immediate intervention arm, PCP participation in the study-specific data collection is not contingent on active engagement with the intervention; any PCP who meets eligibility criteria can complete the self-report questionnaires at baseline and follow-up.

Data collection

Data will be collected in three ways: self-report (PCP surveys and clinic profile data), EHR query (clinic and patient data), and manual chart review (patient data).

PCP Survey

Within each clinic, each participating PCP will complete a baseline and a 12-month follow-up survey. Outcomes will include basic demographics (sex, age, race), care confidence in providing dementia care to patients and their families and other PCP-level variables such as medical specialty, years of practice, tenure at the clinic.

EHR data Extraction

With the Research Methods Core, Drs. [name] and [name] will standardize data between clinics to the extent possible and determine the best approach to create a pooled dataset. Baseline EHR data collection will commence immediately after randomization. Follow-up data collection will be conducted after the 1-year study period is complete.

Clinic level - patient volume (number of active adult patients aged 18+ years during the 12-month study period, total number of primary care clinic visits), number of PCPs, and number of patients at risk of ADRD (active patients aged 55+ with no prior ADRD diagnosis), total number of visits, visits by PCP and provider type, and aggregate counts of new diagnoses (MCI, ADRD, other dementia) based on the ICD-10 codes for these diagnoses. Total patient volumes for patients aged 55-64 and 65+ will be used for clinic-based calculations of the cumulative incidence and prevalence of MCI, ADRD, and dementia.

Patient Level - The goal of this analysis is to determine whether patients with diagnosed ADRD received healthcare consistent with current quality of care standards. Eligible clinic patients are active clinic patient with prevalent ADRD as of the first day of the 12-month baseline [or follow-up] surveillance interval, age 55 or older at the start of the surveillance interval, at least one primary care clinic visit during the 12-month baseline [or follow-up] surveillance interval.

Data extraction domains

- 1. Demographics age, sex, marital and employment status/income, education, language(s) spoken, health insurance
- 2. Comorbidities hypertension, type 2 diabetes, hyperlipidemia, obesity, heart disease, stroke, sleep apnea, and smoking
- 3. Neuroimaging orders

- 4. New prescriptions for potentially beneficial drugs for ADRD symptoms (e.g., cholinesterase inhibitors, N-methyl-D-aspartate antagonists, antidepressants, and antipsychotics) in clinics that track such information in their EHR.
- 5. ADRD quality of care measures, as reported during the Clinic Profile Interview with clinic directors or administrative leadership.
- 6. Quality of care outcomes will be based on existing quality indicators. These comprise 5 domains of care for patients diagnosed with dementia: annual cognitive assessments, annual evaluation of functional status, annual behavioral and psychiatric screening, advance care directives, pharmacological treatment changes.

Manual Medical Chart review

The manual chart review (MCR) will serve to capture details that cannot be extracted from the EHR, and to validate accuracy of patient-level EHR data. It will be conducted once at the 12 month follow-up and will cover both the baseline and 12-month follow-up timepoints for a random selection of at least 20 patients per clinic per time point to 1) document ADRD screening rates and 2) ascertain whether patients with diagnosed ADRD had the quality of care outcomes listed in data collection table above.

- 10 randomly selected patients eligible for cognitive screening will be reviewed to document ADRD screening rates within the EHRs at each site. Screening for MCI or dementia (e.g., Mini-Cog or AD8) may not be captured if the PCP does not use Annual Wellness Visit, Cognitive Assessment and Care Planning, Advanced Care Planning, or Neurobehavioral Status Exam CPT codes.
- 10 randomly selected patients with a previous dementia diagnosis will be examined to assess healthcare quality metrics such as completion of advanced directives, which are not always captured by the Advanced Care Planning CPT codes.

INTACT Intervention

The INTACT Intervention has two components: 1) provide a training for Primary Care Providers (PCPs) training in screening, diagnosis, and care for ADRD and 2) at the clinic level provide a workflow model for cognitive evaluation and setting a plan for the newly diagnosed patient. The INTACT intervention lasts 12 months and Continuing Medical Education credits will be available to PCPs who complete the INTACT training program.

Part 1 PCP training

The INTACT program is composed of 5 online sessions, 4 quarterly webinars and a resource packet. The intervention will be delivered over a period of 12 months, 5 PCP training sessions are designed to be delivered over four months.

Training Sessions

INTACT PCP online training program has 3 didactic sessions and 2 additional sessions focusing on the implementation of the training content in the clinic's unique operational and clinical workflow.

- Session 1: Make a diagnosis of cognitive impairment. An efficient framework for evaluating memory and other cognitive concerns in the primary care setting
- Session 2: Set a plan for the newly diagnosed patient. Structure a discussion about a new diagnosis of mild cognitive impairment including words to use, talking about prognosis, and how to provide high quality community resources to support patients and families.
- Session 3: Manage dementia as it progresses. Medications to treat cognitive impairment, managing agitation, advance care planning, and more.
- Session 4: Integrating the sessions' content into the clinical workflow
- Session 5: Follow-up on session 4 and check on integration of INTACT content into the clinical workflow

Webinars

[name] will convene 4 quarterly webinars for PCPs during the 12-month intervention period. Topics will address 1) Driving and dementia; 2) Communication tips for someone with dementia; 3) Eating and drinking in advanced dementia; and 4) Advance care planning for dementia. [name] will also work with the clinics to identify and incorporate additional topics of interest.

Part 2 In-clinic workflow to facilitate cognitive evaluations

INTACT has developed an in-clinic workflow to facilitate cognitive evaluations that is comprised of the following items. Clinics will be given access to them and receive support on how to implement them:

- a) **Culturally informed educational material** (clinic and PCP levels) for the clinic to distribute to Al/AN patients and families to provide appropriate patient education on ADRD. Such materials include brochures and a short documentary to be played in waiting rooms
- b) Resource lists tailored for each clinic location
- c) Dementia Advance Care Directive (PCP level) is available for free. The directive describes the stages of dementia and offers choices regarding personal goals for medical care at each stage, making it easier for patients to share their views with loved ones who may need to make difficult decisions on their behalf.

Continuing Medical Education (CME)

CME credit for the 4 educational sessions will be offered through the Washington State University Elson S. Floyd College of Medicine

AIM 3: EVALUATE INTACT

Analysis

Analyses will be conducted by using the Stata and R statistical software packages. Inferential results will be presented as point estimates with 95% confidence intervals.

PCP Outcomes (Aim 2)

PCP self-efficacy, care confidence, and knowledge scores derived from multiitem scales will be modeled as continuous data. PCP practice behavior will be analyzed as a dichotomous outcome.

We will use hierarchical regression models with a random intercept for clinic; model specification will reflect that all PCPs within a clinic share the same intervention status. Linear hierarchical models will be used for continuous outcomes and logistic hierarchical models for binary outcomes. The intervention effect will be interpreted as the fixed effect for the INTACT × time (baseline vs. follow up) interaction. We will analyze PCP-specific outcomes using 2 approaches: a within-PCP change analysis and a within-clinic change analysis. For the analysis of within-PCP change, we will restrict the dataset to PCPs who participate in both baseline and follow-up data collection. These models will specify longitudinal data with 2 time points per PCP. Here, the INTACT × time interaction term will be interpreted as the intervention's effect on individual PCPs over time. For the analysis of within-clinic change, the dataset will include all PCPs who participate in data collection at baseline or follow-up regardless of whether they participate in both. The INTACT × time interaction term will be interpreted as the intervention's effect on the clinic environment. Primary analysis will not adjust for covariates. Secondary analyses will adjust for the same set of clinic covariates selected a priori, as above, and for clinic- and PCP-level covariates observed to be unbalanced between groups by chance alone.

Clinic Outcomes (Aim 3)

Incidence rates of new MCI, ADRD, and other dementia diagnoses will be estimated at each clinic for the 12-month intervention period using HER data. All patients aged 55+ who are at risk of the outcome during the study will be included. Poisson regression models will be used to estimate the effect of the intervention on changes in diagnosis rates for MCI, ADRD, and other dementia between intervention and control arms. Poisson models will include number of person years as an offset term. We will be parsimonious in our choice of adjustment variables, but will consider patient volume, state, and type of

facility if an imbalance is apparent after randomization. If we find evidence of an imbalance in covariates between study arms, we will adjust for those variables in the regression analysis.

Patient Outcomes (Aim 3)

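### PCPs who join after randomisation give follow-up data only yet enter the within-clinic analysis, leaving its INTACT × time estimate open to arm-dependent recruitment

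*Combined protocol and SAP*

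**What the plan says.** Under Randomization: "Randomization will occur at the clinic level after completion of the PCP baseline data collection". Under PCP approach and eligibility, enrolment nevertheless stays open, since "any PCPs employed at the clinic can join the study at any time", and "Those joining after randomization will not be asked to complete the baseline survey". Anyone who joins late therefore does so after allocation and supplies a follow-up survey at most.

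On the arms, the Study Design overview says: "Each clinic will be randomized either to the immediate intervention or to a wait-list control arm". The note on immediate intervention arm engagement adds that in intervention clinics "clinic leadership will announce their participation in INTACT and will encourage all PCPs to participate in the programmatic elements", and that "All PCPs employed at the clinic at any time during the 1-year study period are invited to engage with all aspects of the intervention". No blinding of PCPs is described.

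PCP Outcomes (Aim 2) sets out two analyses. For within-PCP change, "we will restrict the dataset to PCPs who participate in both baseline and follow-up data collection". For within-clinic change, "the dataset will include all PCPs who participate in data collection at baseline or follow-up regardless of whether they participate in both". The second INTACT × time term is read as an effect on the clinic environment. Neither analysis is named as the primary one, and the primary models carry no covariates. Nothing limits the number of late joiners, reports them by arm, or plans an analysis without them.

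The PCP Survey section says that each participating PCP completes both a baseline and a 12-month survey. That does not fit with late joiners skipping the baseline.

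**The concern.** Clinic randomisation balances, in expectation, the PCPs recruited before it. It gives no such protection for people who choose to take part afterwards, when the arm can influence who comes forward. Here the training is open and the control is a wait-list, so it is a reasonable inference, though not stated, that late joiners know their arm. Late entry is not limited to new hires: a PCP who ignored the first invitation is counted as refusing, yet may still join later.

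The INTACT × time term removes arm differences among people represented at baseline. Late joiners appear only in the follow-up mean, so any arm difference in who they are passes straight into the estimate. It would then be read as an effect of the programme on the clinic, in an analysis that may be the headline result for Aim 2.

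**Working it through.** **Inputs from the documents.** 28 clinics, 14 in the immediate arm and so 14 on the wait-list. An average of 5 PCPs per clinic at each time point, so 70 per arm. Alpha 0.05 (sidedness not stated; two-sided assumed). ICC ρ from 0.01 to 0.05. 80% power for d as low as 0.5 on PCP outcomes.

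**Step 1: reproduce the plan's figure.** For a comparison at one time point, SE = √[2(1 + 4ρ)/70].
- ρ = 0.01: SE = √(2.08/70) = 0.172; detectable d = 2.80 × 0.172 = 0.483 (0.502 with t on 26 df).
- ρ = 0.05: SE = √(2.40/70) = 0.185; detectable d = 0.519 (0.539 with t).

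The stated 0.5 therefore reproduces, as a single-time-point comparison.

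**Step 2: SE for the analysis at issue.** The planned effect is a difference in changes. With different respondents at each time and a constant clinic effect, the clinic effect cancels and SE = √[4(1 − ρ)/70].
- ρ = 0.01: √(3.96/70) = 0.238.
- ρ = 0.05: √(3.80/70) = 0.233.

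Multiplying by 2.80 gives a detectable d of 0.67 to 0.65.

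**Step 3: bias.** Let f be the late joiners' share of follow-up respondents and s their difference, in SD, from PCPs enrolled before randomisation. Subscripts I and C denote the arms. With no true effect, the INTACT × time estimate is off by

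bias = f_I·s_I − f_C·s_C.

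The documents give neither f nor s, so these scenarios are assumptions:
- 30% against 20% late joiners, both shifted by 0.5 SD: 0.15 − 0.10 = 0.05 SD.
- 20%, shifted by 0.5 SD, in one arm only: 0.10 SD.
- 40%, shifted by 0.5 SD, in one arm only: 0.20 SD.
- Equal share and equal shift in both arms: 0.

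For scale, at 5 PCPs per clinic one late joiner is 20% of that clinic's follow-up sample.

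**Step 4: type I error.** Rejection probability = Φ(b/SE − 1.96) + Φ(−b/SE − 1.96), with SE 0.233 to 0.238.

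| Net bias b | Share of the 0.5 SD planning effect | b/SE | Two-sided type I error |
|---|---|---|---|
| 0 | 0% | 0 | 5% |
| 0.05 SD | 10% | 0.21 | 5.5% |
| 0.10 SD | 20% | 0.42-0.43 | 7% |
| 0.20 SD | 40% | 0.84-0.86 | 13-14% |

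A negative bias of the same size gives the same two-sided rate, with the false result favouring the wait-list. A clinic effect that drifts over the year would raise the SE and lower these rates. Positive correlation between repeat surveys from the same PCPs would work the other way.

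**The case against.** The open cohort is deliberate: the study is framed at clinic level, new hires are meant to receive the intervention, and staff turnover belongs to a question about the clinic environment. This stands as a reason to keep the analysis. It does not cover survey participation that depends on arm.

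The within-PCP analysis already leaves out every late joiner, so a spurious effect produced by them would not appear there. That is a real but partial check: requiring both surveys makes it a completer set, with its own attrition risk, and the plan does not rank it first.

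A reader might infer that training and CME credit draw PCPs into the survey in the intervention arm and so push the result upward. The documents do not support this. Survey participation is expressly separate from engagement with the training, CME credit goes to those who complete the training, and no survey recruitment that differs by arm is described. Names of participating PCPs are also withheld from clinic leadership, which limits pressure to enrol. The direction is open too: the five sessions are designed to run over four months, so later hires may have had little exposure and could lower the intervention mean.

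A reader might also take the SE of 0.172 behind the plan's d = 0.5 and arrive at error rates of about 9% and 20% for biases of 0.10 and 0.20 SD. That SE belongs to a single-time-point comparison, not to the INTACT × time term.

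**Conclusion.** The concern holds for one of the two PCP survey analyses. Late entry without a baseline survey, and inclusion in the within-clinic dataset, are explicit; awareness of the arm is a strong inference. Bias is possible rather than shown, it can go either way, and its size cannot be derived from the documents. The 5.5% to 14% range rests on the assumed net biases of 0.05 to 0.20 SD, on 5 PCPs per clinic at each time point, and on the repeated cross-section SE. It would be wrong to extend the point to diagnoses, prescribing or chart-based quality of care: those outcomes come from the EHR and chart review and do not directly depend on which PCPs answer the survey. The plan's real gap is that it neither names a primary PCP analysis nor accounts for late joiners. Closing it is a cheap improvement.

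**What to change.** In PCP Outcomes (Aim 2):
- Name PCPs who consented before randomisation as the primary analysis set for all PCP outcomes. Use every survey they supply, so that those with only a baseline are not dropped.
- Keep the open-cohort within-clinic analysis as secondary.
- Report the number and characteristics of late joiners by arm.
- Refit the within-clinic model without late joiners as a sensitivity analysis.

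Also reconcile the PCP Survey section, which has every participating PCP completing a baseline, with the eligibility note that exempts late joiners.

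The change is to SAP wording and needs no new data collection. Its downside should be stated in the SAP. The primary analysis will have fewer follow-up surveys, which matters at about 5 PCPs per clinic. It will also depend more on retaining the original PCPs, and retention may itself differ by arm, so it too should be reported by arm.

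### The diagnosis-rate model omits the randomisation batches and names no clinic-level variance term; for the PCP and patient models the omission of batch matters little

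*Combined protocol and SAP*

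**What the plan says.** **Design.** Under Randomization, "Clinics will be randomized in batches with at least 2 clinics per batch", so that clinics launch together with each arm represented. Under Recruitment, the study is "implemented in a staggered fashion creating at least three cohorts". The same section sets a minimum of two clinics per cohort. The trial has 28 clinics, and the Randomization section refers to "For the 14 clinics randomized to the immediate intervention arm", which implies 14:14 overall. Neither the batch sizes nor the allocation ratio within a batch is given.

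**PCP outcomes.** "We will use hierarchical regression models with a random intercept for clinic". The effect is the INTACT × time interaction, and the primary analysis is unadjusted.

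**Clinic outcomes.** Incidence rates of new MCI, ADRD and other dementia diagnoses are estimated for the 12-month intervention period and compared by Poisson regression. "Poisson models will include number of person years as an offset term". Patient volume, state and facility type may be added if imbalanced. No clinic effect, overdispersion term, batch or cohort is named.

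**Patient outcomes.** These follow the PCP approach, with clustering of patients within PCP added.

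**Power.** The Power section covers PCP and patient outcomes only. It contains no batch term and no calculation for diagnosis rates.

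**The concern.** Batch restricts the randomisation and also fixes the calendar year in which a clinic is observed. An analysis that leaves it out does not reflect how treatment was allocated.

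The consequence depends on the model. Where an effect is estimated from one period, differences between batches in calendar time or launch conditions remain in the clinic rates. If the model has a clinic-level variance term, they are counted as noise although the design has balanced them, and precision is lost. If it has no such term, as in the Poisson model as written, the standard error comes from the event counts alone and ignores variation between clinics altogether. The intervals are then too narrow. New diagnoses are the whole of the clinic-level evidence in Aim 3, and they rest on only 28 randomised units.

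**Working it through.** **1. The plan's own figures.** The inputs from the Power section are 5 PCPs or 50 patients per clinic (m), ICC 0.01 to 0.05, alpha 0.05 (two-sided assumed) and 80% power, with 14 clinics per arm. For a comparison at one time point, the detectable d = (1.960 + 0.842) × √{(2/14)[ICC + (1 − ICC)/m]}.
- PCP: 2.802 × √(0.1429 × 0.208) = 0.48 at ICC 0.01, and 2.802 × √(0.1429 × 0.240) = 0.52 at ICC 0.05.
- Patient: 2.802 × √(0.1429 × 0.0298) = 0.18, and 2.802 × √(0.1429 × 0.069) = 0.28.

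These agree with the stated 0.5 and 0.2 to 0.3. The figures reproduce without batch, and from a single-time-point formula rather than the planned interaction.

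**2. Poisson model as written.** The documents give no event rate, between-clinic variation or batch variance. The assumptions are 50, 200 or 500 at risk per clinic, 2% per year (μ = 1, 4 or 10 events), a between-clinic coefficient of variation (CV) of 0.5, a share b of the clinic variance due to batch, and 1:1 pairs.

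Relative to a pure Poisson count, the variance that affects the arm comparison is 1 + μ·CV²·(1 − b). At μ = 4:
- b = 0: 1 + 4 × 0.25 = 2.0; type I error = 2[1 − Φ(1.96/√2.0)] = 16.6%
- b = 0.5: 1.5; 2[1 − Φ(1.96/√1.5)] = 11.0%
- b = 0.9: 1.1; 2[1 − Φ(1.96/√1.1)] = 6.2%

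Simulated type I error (20,000 runs per setting):

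| At risk per clinic | b = 0 | b = 0.5 | b = 0.9 |
|---|---|---|---|
| 50 | 7.2% | 5.7% | 5.2% |
| 200 | 15.9% | 11.1% | 6.3% |
| 500 | 29.4% | 19.1% | 8.0% |

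A second simulation with 200 at risk, a 2% rate and CV 0.5 gave 12% to 22%. I rest on the table because it agrees with the closed form. Both show intervals that are too narrow.

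**3. Count model with a clinic-level variance term but no batch.** The estimated dispersion is now the total, 1 + μ·CV², while the comparison is affected only by the within-batch part. The standard error is overstated by √{(1 + μ·CV²)/(1 + μ·CV²(1 − b))}. With b = 0.5:
- μ = 1: √(1.25/1.125) = 1.05
- μ = 4: √(2.0/1.5) = 1.15
- μ = 10: √(3.5/2.25) = 1.25

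In the second simulation, adding batch at 200 at risk cut the median standard error by about 5% to 15%. Leaving it out therefore overstates it by 1/0.95 to 1/0.85, or 5% to 18%. Type I error with batch included was about 4% to 6%.

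**4. Cost of fixed batch effects.** With 14 pairs the degrees of freedom fall from 28 − 2 = 26 to 27 − 14 = 13. The t multiplier rises from 2.056 to 2.160, a factor of 1.051. Net of this, the ratios in step 3 become 1.05/1.051 = 1.00, 1.15/1.051 = 1.10 and 1.25/1.051 = 1.19. At μ = 4, break-even needs a dispersion reduction of (1 − 1/1.051²) × 2.0 = 0.19 out of the clinic part of 1.0, so batch must hold about 19% of clinic variance. Three batches leave 24 degrees of freedom (multiplier 2.064), at almost no cost.

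**5. PCP and patient models.** Each clinic belongs to one batch, so a stable batch difference is present at both time points and drops out of the interaction. With residual variance 0.95, the interaction's standard error for 5 PCPs is √[(4/14)(0.95/5)] = 0.233 whether none, half or all of a clinic variance of 0.05 is due to batch. A batch intercept therefore changes nothing.

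If batches differ in their change over time (variance 0.02, 50 patients, 1:1 batches), the model's residual is [56 × 49 × 0.95 + 26 × (50 × 0.02 + 0.95)]/(56 × 49 + 26) = 0.959. The ratio of model to true standard error is √(0.959/0.95) = 1.005, with type I error 4.9%.

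**The case against.** **The effect is a comparison of changes.** This is the strongest objection, and it stands for PCP and patient outcomes: batch has next to no influence on the planned interaction, and a batch intercept would be idle. For linear models the cancellation is direct; for the logistic models it holds on the log-odds scale.

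**Diagnosis rates may also be meant as changes.** The Clinic Outcomes text does speak of changes in diagnosis rates, and baseline EHR data are collected. But the rates are defined for the intervention period, and no baseline or time term is specified for the Poisson model. If a baseline year is intended, the SAP should say so; stable batch differences would then cancel there too.

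**The main defect is the missing clinic-level variance, not batch.** This stands in part. A batch term alone would not repair the intervals, as the b = 0 column shows, so the two terms belong together.

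**Stronger readings that the documents do not support.**
- A reader might infer that standard errors are inflated throughout, by up to 1/√(1 − 0.5) = 1.41 when batch holds half the clinic variance. That treats a clinic summary as free of sampling error. Even at a single time point with ICC 0.01 to 0.05, a half share gives 1.2% to 5.7% for PCP outcomes and 9.6% to 25% for patient outcomes, and the planned analysis is not a single-time-point one.
- A reader might infer that the diagnosis-rate intervals are too wide. As written, the model errs in the other direction.
- A reader might infer bias. With 1:1 batches there is none. The protocol does allow odd-sized batches, in which arm ratios would differ and batch differences would no longer balance exactly, but it does not say that these will be used.

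**Conclusion.** The point holds, chiefly for the clinic diagnosis-rate model. The randomisation is restricted by batch, no model reflects it, and in the Poisson model nothing removes batch differences or allows for variation between clinics. As written, its intervals are likely too narrow: type I error is about 6% to 16% in the central assumed case. After clinic-level variance is added, omitting a batch effect that holds half of it overstates the standard error by roughly 5% to 20%, with about 25% at 10 expected events per clinic before any loss of degrees of freedom. If batch holds none of it, there is nothing to gain.

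For PCP and patient outcomes the expected gain is about 0.5% of the standard error in 1:1 batches, so no conclusion there depends on batch.

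All sizes rest on assumed event rates, between-clinic variation and batch shares, because the documents give none of these, nor the batch sizes or ratios.

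**What to change.** 1. **Clinic Outcomes.** Specify a count model with arm, the person-years offset, randomisation batch, and a clinic random effect or overdispersion term. Use a random intercept for batch, or fixed effects if batches prove few and large. State whether the baseline year enters the model.
2. **Randomization.** State the planned batch sizes and the allocation ratio within a batch, including how odd-sized batches are handled.
3. **PCP and patient models.** Either say that batch is left out because stable differences cancel in the interaction, or include it as batch-by-time. Do not add a batch intercept alone.
4. **Inference.** State the reference degrees of freedom. A randomisation test that respects the batches is an acceptable alternative.

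The cost is SAP wording; batch is known from the randomisation, so no new data are needed. With 14 fixed pairs, intervals widen by about 5% if batch explains nothing; a random intercept avoids most of this. Adding the clinic-level term will probably widen the diagnosis-rate intervals, which corrects the present understatement.
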